6. STUDY PROCEDURES

6.1 Schedule of Evaluations

Table 1. Schedule of Evaluations, Phase 1, Prisoners.

Assessment	Baseline and Enrollment: (Day-30 to Day -1)	Focus Group Visit 1 (Day 0)
Inclusion/ Exclusion	X	
Informed consent form	X	
Demographics	X	
Novaco Anger Scale – Provocation Inventory	X	
MINI (screening)	X	
Physical Activity Readiness Questionnaire	X	
Payment		\$20

Table 2. Schedule of Evaluations, Phase 1, Stakeholders.

Assessment	Baseline and Enrollment: (Day-30 to Day -1)	Baseline, Enrollment, Visit 1 (Day 0)
Inclusion/ Exclusion	X	
Informed consent form		X
Demographics		X
Payment		\$20

Table 3. Schedule of Evaluations, Phase 2.

Assessment	Type of Assessment	Baseline1, Visit 1 (Day 0)	After initial class	After each class	Wk 5	Wk 10	Wk 14	Wk 18
Inclusion/ Exclusion	Interview, pre-randomize	X						
Informed Consent Form	Pre-randomize	X						
Enrollment/ Randomization	Interview	X						
CEQ	Self-report		X					
CSQ-8	Self-report					X		
Qualitative Interview	Interview					X	X (yoga only)	
Homework Questionnaire	Self-report			X				
Injuries due to yoga	Self-report			X				
SAFTEE- GI	Interview	X			X	X		X
Novaco Anger Scale- Provocation Inventory	Self-report	X			X	X		X
Aggression Questionnaire- Short Form	Self-report	X			X	X		X
Behavioral Infractions in Prison	Record Review	X			X	X		X
Patient Health Questionnaire-9	Self-report	X			X	X		X
PROMIS Anxiety	Self-report	X			X	X		X
SF-12 from RAND Medical Outcomes Study	Self-report	X			X	X		X
Anger Rumination Scale	Self-report	X			X	X		X
Experiences Questionnaire	Self-report	X			X	X		X
Stroop Color and Word Test	Task	X			X	X		X
MINI (screening)	Interview	X						

Assessment	Type of Assessment	Baseline1, Visit 1 (Day 0)	After initial class	After each class	Wk 5	Wk 10	Wk 14	Wk 18
Physical Activity Readiness Questionnaire	Self-report	X						
Life Events Checklist/PTSD Checklist	Self-report	X						
Treatment History Interview	Interview	X			X	X		X
International Physical Activity Questionnaire	Self-report	X			X	X		X
Payment					\$20	\$20	\$20	\$20

Abbreviations: timepoints: Wk5, Wk10, Wk18 = Week 5, Week 10, Week 18.

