For all follow-up assessments, research staff will make every effort to conduct the assessment within one week before or one week after the exact due date of the assessment. However, because all data can be analyzed with modern statistical methods regardless of whether it was collected inside that window, RAs will still collect data if possible even if it is later than that two-week window. We will record optimum date for the assessment as well as the actual date of the assessment.

Participants will complete a brief assessment after each class that they attend.

In addition, all participants will be assessed at: baseline, 5 weeks (mid-intervention), 10 weeks (post-intervention), 14 weeks (yoga group participants only), and at 8 week follow-up. In addition to demographics, we will assess acceptability of the intervention conditions, safety of the yoga condition, anger and aggression, secondary outcomes (depression and anxiety symptoms, general functioning), potential intervention mechanisms of action (anger rumination, decentering, impulsivity), and other descriptive characteristics (trauma history, treatment utilization, physical activity levels).

In the event that a participant is released back into the community before they complete all of their study assessments, we will complete them in the community. We will aim to complete all of these follow-up assessments by telephone. However, there may be some circumstances that might make it difficult for a participant to complete the follow-up assessment by telephone (e.g., limited phone minutes, enrollment in a residential treatment program). In such cases, we will complete the follow-up assessment in person in our offices at Brown University or in the facility where the participant is located (e.g., residential treatment facility, with facility approval). Additionally, if a participant is transferred to another facility at RIDOC, we will complete their assessments at the other facility (e.g., Men's Maximum Security) with RIDOC approval.

Please see table 3 for a list of all assessments to be completed at each visit.

6.2.7 Completion/Final Evaluation - Phase 2

Even if prisoners drop out of study treatment, we will attempt to collect data at all assessment points if prisoners agree to it.

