7.2 Specification of Safety Parameters

Safety issues will be minimal in Phase 1 given that participation involves only a single focus group, no yoga classes, and no formal assessment of suicidality. However, should an issue arise (e.g., a voluntary report of suicide ideation), staff would manage it in the same way that they would manage it in Phase 2.

Please see Table 4 for a summary of safety issues, how they are assessed, when they are assessed, and relevant staff actions.

Table 4. Assessment and Management of Safety Issues, Summary, Phase 2

Safety Issue	How assessed	When Assessed in Phase 2	Relevant Research Staff Actions
Suicide or homicidal ideation	PHQ-9 Participant report to research staff	BL, wk5, wk10, wk18 Any point	Immediate clinical assessment as described in DSMP
Injuries due to yoga	Structured self-report	Weekly during first 10 weeks	Follow until resolution; may result in changes to yoga instructor manual
Other AEs	SAFTEE Participant report to research staff	BL, wk5, wk10, wk18 Any point	If related to study participation, follow resolution; potential changes to procedures particularly if AE is also unexpected

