Unanticipated problems will be recorded in the data collection system throughout the study. Study staff will record all reportable events with start dates occurring any time after informed consent is obtained until 8 weeks (i.e., follow-up assessment after the last day of class participation). Each time participants attend classes, we will inquire about injuries due to study participation. At midpoint, endpoint, and at week 8 follow-up, study staff will administer the SAFTEE in order to inquire about the occurrence of AE/SAEs during the previous 8-10 weeks. SAEs related study participation will be followed for outcome information until resolution or stabilization.

Characteristics of an adverse event will include: a) relationship to study intervention, b) expectedness of SAEs, and c) event severity.

Relationship to Study Intervention

To assess relationship of an event to study intervention, the following guidelines are used:

1. Related (Possible, Probable, Definite)
 - a. The event is known to occur with the study intervention.
 - b. There is a temporal relationship between the intervention and event onset.
 - c. The event abates when the intervention is discontinued.
 - d. The event reappears upon a re-challenge with the intervention.
2. Not Related (Unlikely, Not Related)
 - a. There is no temporal relationship between the intervention and event onset.
 - b. An alternate etiology has been established.

Relatedness of SAEs

The Study PI and Independent Monitoring Committee will be responsible for determining whether an SAE is expected or unexpected. An adverse event will be considered unexpected if the nature, severity, or frequency of the event is not consistent with the risk information previously described for the intervention. The risk information to assess expectedness can be obtained from preclinical studies, the investigator's brochure, published medical literature, the protocol, or the informed consent document.

Expected AEs for this study include:

- Any event that may be reasonably anticipated to occur as a result of the study procedure (i.e., mild aches or pains following a yoga class)

Severity of Event

The following scale will be used to grade adverse events:

1. Mild: no intervention required; no impact on activities of daily living (ADL)
2. Moderate: minimal, local, or non-invasive intervention indicated; moderate impact on ADL

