Acceptability and Feasibility. Intervention credibility and patient expectations for intervention success at baseline will be measured with the Credibility Expectancy Questionnaire (CEQ)²³; this is administered after their initial class. The Client Satisfaction Questionnaire (CSQ-8)²⁴ will be used post-treatment to assess satisfaction with treatment. We will also use qualitative responses to a detailed post-treatment interview to gain participants' feedback about intervention components and research procedures. Finally, it is critical that the amount of yoga practice at home be measured as accurately as possible. Participants will complete a yoga homework questionnaire on a weekly basis. The tool will yield three indices of home practice: frequency of extended home practice, minutes of extended home practice, and frequency of micro home practice.

Participant safety. After each homework questionnaire, we will ask participants in the yoga arm only whether they experienced any injuries as a result of yoga practice. At each follow-up, we will administer the Systematic Assessment of Treatment-Emergent Events – General Inquiry (SAFTEE)²⁵ to all participants. This allows us to systematically assess number of adverse events, severity, and resulting impairment. Finally, any time a participant reports an adverse event to any staff member, a research assistant will talk with the participant to ascertain information for recording of the adverse event. For adverse events ascertained by any of these three possible methods, the research assistant gets information on what happened, start and stop dates, severity, functional impact, interactions with healthcare professionals, perceived cause, and possible relation to study participation. For more information and details on coding of AEs, please see DSMP.

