9.5 Outcomes

9.5.1 Primary Outcome.

The primary outcomes are acceptability, feasibility, and safety.

Target treatment development outcomes. We monitor treatment development outcomes (see Table 6) throughout the trial. Target outcomes were chosen on face validity, clinical experience, and, when available, relevant clinical literature. At 3 time points throughout the RCT (i.e., after enrolling 10, 20, and 40 participants), the scientific team will convene to discuss how our actual procedural outcomes compare to the target outcomes. Discrepancies will result in: 1) investigation (using qualitative or other data) of the reason for the failure to meet this outcome; and 2) discussion amongst the research team. Depending on the nature of the discrepancy, we may modify recruitment procedures, assessment procedures, instructions to participants, instructor training procedures, or other aspects of the trial. Ultimately, failure to meet these outcomes could result in a decision not to write a grant proposal for a large-scale RCT; in other cases, it may inform the design of a subsequent RCT.

Primary data analyses will be focused on feasibility and acceptability (see Table 6) using intent-to-treat population. Study measures and endpoints will continue to be collected for all enrolled participants if they are willing, even in the event of premature discontinuation of the study intervention.

Table 2. Target Outcomes

Description (Assessment method)	Target
Feasibility and Acceptability-- Hatha yoga, Health education	
Acceptability (qualitative interview)	Most feedback positive; few substantive negative comments. Negative comments used to enhance procedures.
Credibility at baseline (CEQ)	Average > 50 (i.e., midpoint score between low and high credibility) on subscale
Expectancy at baseline (CEQ)	Average > 50 (i.e., midpoint score) on subscale
Program satisfaction (CSQ-8)	Average total score > 24
Home practice (homework questionnaire)	70% of yoga participants engage in practice at least 2 times per week for 6/10 weeks.
Class attendance	70% of all participants complete 6/10 classes in the RCT
Instructor adherence (Adherence measures)	Yoga instructors and HE instructors achieve at least 80% adherence on a random subset of classes taught
Class size	70% of classes have 4 or more participants.
Safety	
Adverse events (SAFTEE; injuries due to yoga)	No serious adverse events or injuries that are possibly, probably, or definitely related to study participation.

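### Sections 9.1.2 and 7.4 disagree on who gets the post-class injury question; if it is yoga-only, the all-source adverse event count is not comparable between arms

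*Combined protocol and SAP*

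**What the plan says.** Four places describe the recurring injury question.

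- Section 9.1.2 (Participant safety) ties it to the homework questionnaire and restricts both the respondents and the subject: "we will ask participants in the yoga arm only whether they experienced any injuries as a result of yoga practice".
- Section 7.4 has no such restriction: "Each time participants attend classes, we will inquire about injuries due to study participation". DSMP section 3.2 repeats that sentence. Both arms attend classes.
- Table 3 has a row named "Injuries due to yoga", marked for after each class. It carries no yoga-only tag, although the week 14 interview in the same table does.
- Table 4 gives the timing as "Weekly during first 10 weeks".

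Section 6.2.6 adds, for both arms: "Participants will complete a brief assessment after each class that they attend". It does not say what the form contains.

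SAFTEE goes to everyone: "At midpoint, endpoint, and at week 8 follow-up, study staff will administer the SAFTEE in order to inquire about the occurrence of AE/SAEs". Section 9.1.2 then handles all reports alike, "For adverse events ascertained by any of these three possible methods", the methods being the yoga injury question, SAFTEE and spontaneous report to staff. The target outcomes table in 9.5.1 combines two of these in one row, which begins "Adverse events (SAFTEE; injuries due to yoga". Safety is one of the primary outcomes named in 9.5.1.

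**The concern.** The passages differ on who is asked (the yoga arm, or anyone attending class) and on what is asked (injury from yoga practice, or injury from taking part in the study). Staff working from 9.1.2 and staff working from 7.4 would collect different data on a primary outcome.

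Under 9.1.2, the arms also have unequal opportunity to report. A minor ache that a yoga participant mentions after class is recorded. The same ache in a health education participant is recorded only if it is recalled at a SAFTEE visit or volunteered. If all sources are added and the totals set side by side, part of any difference reflects how often people were asked. This bears on two uses: what is carried into the larger trial, and the review against pre-study expectations required by DSMP 7.6. Section 7.1 expects no adverse events in health education, and asking that arm less often makes the expectation easier to confirm.

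**Working it through.** The plan gives no adverse event rate, detection rate or safety sample size calculation, so there is no stated figure to reproduce. The check is a count of inquiries and then an illustration.

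**Inputs from the documents**

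- Post-class question: up to 10 (weekly classes for 10 weeks; Table 4).
- SAFTEE after baseline: 3 (weeks 5, 10 and 18; Table 3), both arms.
- Attendance threshold for adherence: 6 of 10 classes (section 5.4).

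**Solicited inquiries per participant after baseline** = post-class questions + SAFTEE visits

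| Reading | Classes attended | Yoga | Health education |
|---|---|---|---|
| 9.1.2 (yoga only) | 10 | 10 + 3 = 13 | 0 + 3 = 3 |
| 9.1.2 (yoga only) | 6 | 6 + 3 = 9 | 0 + 3 = 3 |
| 7.4 and DSMP 3.2 (all attendees) | 10 | 13 | 13 |
| 7.4 and DSMP 3.2 (all attendees) | 6 | 9 | 9 |

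The SAFTEE gaps are 5, 5 and 8 weeks (0 to 5, 5 to 10, 10 to 18). Section 7.4 gives a look-back of 8 to 10 weeks, so SAFTEE covers the whole period in both arms.

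**What unequal inquiry could do (illustration; s and c are assumptions).** Let s be the chance that SAFTEE picks up an event and c the chance that the post-class question does. Take them as independent, set spontaneous reports aside, and suppose equal true event rates.

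- Recorded share in yoga: 1 − (1 − s)(1 − c). Recorded share in health education: s.
- Ratio r = [1 − (1 − s)(1 − c)] / s.
- s = 0.9, c = 0.3: (1 − 0.1 × 0.7) / 0.9 = 0.93 / 0.9 = 1.03.
- s = 0.5, c = 0.6: (1 − 0.5 × 0.4) / 0.5 = 0.80 / 0.5 = 1.6.
- s = 0.3, c = 0.9: (1 − 0.7 × 0.1) / 0.3 = 0.93 / 0.3 = 3.1.

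Over s and c from 0.3 to 0.9, r therefore runs from 1.03 to 3.1. It applies only to events that a participant would report in answer to the yoga question. If these make up a fraction f of all events, the ratio for the all-source count is [f·r·s + (1 − f)·s] / s = 1 + f(r − 1). This approaches 1 as f falls. The documents give no value for f, and the item in 9.1.2 is narrow.

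Under the 7.4 reading both arms have the same s and c, and the ratio is 1.

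**The case against.** The strongest reply is that the yoga-only question is deliberate. Tables 3 and 4 and the target outcomes table all name yoga injuries, 6.2.6 speaks of the safety of the yoga condition, and 7.1 has yoga instructors watch for injury while expecting no adverse events in health education. Closer surveillance of a known risk in the exposed arm is reasonable. That stands as a defence of the design. It does not remove the contradiction: 7.4 and DSMP 3.2 would then be wrong as written, and the combined count would still draw on a source that one arm lacks.

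A reader might go further and infer that the plan will make yoga look more harmful than health education. The documents do not support that.

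- No between-arm test of adverse events is planned, and no by-arm table is specified. The safety analysis is descriptive, DSMP 7.6 asks only for a summary table, and DSMP 4.2 keeps group-identifying material out of adverse event reports.
- The safety target is absolute (no related serious events or injuries), so more inquiry makes it stricter, not biased as a contrast.
- SAFTEE gives equal solicited ascertainment in both arms, and spontaneous reports are accepted from anyone.

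Nor can the inquiry counts be turned into a percentage of participants with an event by giving every inquiry the same independent yield in both arms. A question about yoga injuries over about a week is not equivalent to a general SAFTEE inquiry over 8 to 10 weeks, and health education classes cannot cause a yoga injury.

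**Conclusion.** The contradiction is established from the text: 9.1.2 differs from 7.4 and DSMP 3.2 on both respondents and content, and Table 3 leaves it open. If 9.1.2 is followed, the all-source adverse event count is not comparable between arms, with up to 13 against 3 solicited inquiries at full attendance and 9 against 3 at 6 of 10 classes.

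The direction is towards more recorded events in yoga. The size cannot be derived from the documents; the 1.03 to 3.1 range rests on assumed detection chances and equal true rates, and the effect on the total may be small because the item is narrow. SAFTEE-only counts are not affected. The matter should be corrected because it concerns how a primary outcome is ascertained and the remedy costs little, but it does not undermine the safety target as the plan states it.

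**What to change.** Reconcile 9.1.2, Table 3, 7.4 and DSMP 3.2 in one of two ways.

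1. **Ask both arms.** Put the 7.4 question, on injuries from taking part in the study, on the post-class assessment for everyone, and amend 9.1.2 and the Table 3 row to match. Keep that scope: an open question about any injury would be a different item and would collect unrelated events in prison.
2. **Keep it yoga-only.** Say so in 7.4 and DSMP 3.2, and tag the Table 3 row.

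Under either option, tabulate adverse events by source (post-class question, SAFTEE, spontaneous report). This is useful even under option 1, because the instructor monitoring in 7.1 is described for yoga only. Under option 2, restrict any side-by-side display of arms to SAFTEE-elicited events.

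Cost: one extra table split and, under option 1, one extra post-class question for health education attendees. Section 6.2.6 already foresees a post-class form for all, but Table 3 and 9.1.2 describe no health education content for it, so a short form may have to be written.

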9.2 Sample Size and Randomization

9.2.1. Sample Size.

This project consists of three phases: In Phase 1, we will conduct focus groups with up to 18 prisoners and 6 prison stakeholders. In Phase 2, we will consent up to 175 prisoners in order to achieve our enrollment goal of 40 prisoners who meet study inclusion for randomization to conditions in the pilot RCT. We will assess feasibility, acceptability, and safety of the interventions and research design, and examine key outcomes within relevant confidence intervals. This phase of the study is not designed to be adequately powered to assess efficacy; rather, it is focused on feasibility, acceptability, and safety.

9.2.2. Treatment Assignment Procedures.

Participants in Phase 2 will undergo randomization. Randomization will be conducted using a blocked stratified randomization scheme. We will stratify patients based on gender and facility (i.e., men’s medium security [n= 20], and women’s combined minimum and medium security [n=20]). Randomization sequences will be generated by computer. Because we cannot bring computers into the prison, we will have someone not associated with the study conceal the group assignments within small opaque envelopes labeled with a number and the strata (for example, male medium 1, male medium 2, etc.). Research assistants will then take the envelopes to the prison, and open them when randomization occurs.

9.3 Definition of Populations

All data analysis will use the intent to treat population and use all available data. There is no per protocol analysis planned.

9.4 Interim Analyses and Stopping Rules

9.4.1 Interim analysis.

There is no interim data analysis plan.

Data analysis of Phase 1 qualitative data will occur during and immediately after data collection in Phase 1.

Data analysis of Phase 2 data will occur after enrolling 10, 20, and 40 participants (for feasibility and acceptability outcomes).

9.4.2 Halting Rules.

If there are any SAEs judged related to the study intervention, we will halt the study intervention until an ad hoc safety review is convened with the DSMB, MPIs, site PI, and other relevant study staff. The safety review will determine whether the study should continue per protocol, proceed with enhanced monitoring, be further investigated, be discontinued, or be modified and then proceed. Subsequent review of serious, unexpected, and related AEs by the DSMB, IRB, the sponsor(s), or relevant local regulatory authorities may also result in suspension of further study interventions. The study sponsor(s) retain the authority to suspend additional enrollment and study interventions/ administration of study product for the entire study, as applicable.

9.5 Outcomes

9.5.1 Primary Outcome.

The primary outcomes are acceptability, feasibility, and safety.

Target treatment development outcomes. We monitor treatment development outcomes (see Table 6) throughout the trial. Target outcomes were chosen on face validity, clinical experience, and, when available, relevant clinical literature. At 3 time points throughout the RCT (i.e., after enrolling 10, 20, and 40 participants), the scientific team will convene to discuss how our actual procedural outcomes compare to the target outcomes. Discrepancies will result in: 1) investigation (using qualitative or other data) of the reason for the failure to meet this outcome; and 2) discussion amongst the research team. Depending on the nature of the discrepancy, we may modify recruitment procedures, assessment procedures, instructions to participants, instructor training procedures, or other aspects of the trial. Ultimately, failure to meet these outcomes could result in a decision not to write a grant proposal for a large-scale RCT; in other cases, it may inform the design of a subsequent RCT.

Primary data analyses will be focused on feasibility and acceptability (see Table 6) using intent-to-treat population. Study measures and endpoints will continue to be collected for all enrolled participants if they are willing, even in the event of premature discontinuation of the study intervention.

Table 2. Target Outcomes

Description (Assessment method)	Target
Feasibility and Acceptability-- Hatha yoga, Health education	
Acceptability (qualitative interview)	Most feedback positive; few substantive negative comments. Negative comments used to enhance procedures.
Credibility at baseline (CEQ)	Average > 50 (i.e., midpoint score between low and high credibility) on subscale
Expectancy at baseline (CEQ)	Average > 50 (i.e., midpoint score) on subscale
Program satisfaction (CSQ-8)	Average total score > 24
Home practice (homework questionnaire)	70% of yoga participants engage in practice at least 2 times per week for 6/10 weeks.
Class attendance	70% of all participants complete 6/10 classes in the RCT
Instructor adherence (Adherence measures)	Yoga instructors and HE instructors achieve at least 80% adherence on a random subset of classes taught
Class size	70% of classes have 4 or more participants.
Safety	
Adverse events (SAFTEE; injuries due to yoga)	No serious adverse events or injuries that are possibly, probably, or definitely related to study participation.
Feasibility and Acceptability—Research Procedures	
Recruitment rate	Average of 6 enrolled per month
Retention rate	80% complete week 10 assessment; 70% complete wk. 18 assessment
Completion of items on assessment instruments	At least 90% of items are completed on each assessment instrument (so each will be valid).

9.5.2 Secondary/ Exploratory Outcomes.

In Phase 2, we will also examine change in key variables over time. This is an exploratory analysis.

Specifically, we will look at change over time the in the following variables. The primary outcome in a subsequent efficacy study is in **bold and underlined**. Secondary outcomes are in standard text. *Potential mechanisms are in italics*.

- **NAS-Provocation Inventory from BL to wk10**; BL to wk18.
- Aggression Questionnaire – Short Form, BL to wk10; BL to wk18.
- Number of behavioral infractions in Prison, BL to wk10; BL to wk18
- PHQ-9, BL to wk10; BL to wk18
- PROMIS Anxiety, BL to wk10; BL to wk18
- SF-12 physical health composite score, BL to wk10; BL to wk18
- SF-12 mental health composite score, BL to wk10; BL to wk18
- *Anger rumination scale, BL to wk10; BL to wk18*
- *Experiences Questionnaire, BL to wk10; BL to wk18*

- *Stroop Color and Word Test, BL to wk10; BL to wk18*

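### Home-practice benchmark: the homework form follows attended classes in the visit schedule but is called weekly elsewhere, so practice in missed-class weeks may go unrecorded

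*Combined protocol and SAP*

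**What the plan says.** The target outcomes table in 9.5.1 sets the home-practice target as "70% of yoga participants engage in practice at least 2 times per week for 6/10 weeks" and names the homework questionnaire as its source. Section 9.1.2 explains why the measure matters: "it is critical that the amount of yoga practice at home be measured as accurately as possible".

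The timing of the form is given in two ways.

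- **Tied to classes.** Table 3 (section 6.1) marks the row "Homework Questionnaire" in the column for after each class, and it has no weekly column. Section 6.2.6 says: "Participants will complete a brief assessment after each class that they attend".
- **Weekly.** Section 9.1.2 says: "Participants will complete a yoga homework questionnaire on a weekly basis".

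The yoga-injury item has the same split. Table 3 places it after each class, and section 7.4 says: "Each time participants attend classes, we will inquire about injuries due to study participation". Table 4 (section 7.2) lists it as weekly for the first 10 weeks. Section 9.1.2 attaches it to the homework form: "After each homework questionnaire, we will ask participants in the yoga arm only whether they experienced any injuries as a result of yoga practice".

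Section 9.3 specifies the intent-to-treat population and all available data. Neither it nor any other section says how a week without a class is collected or scored.

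**The concern.** Yoga classes are weekly, so the two descriptions agree for anyone who attends every class. They part only in a missed-class week. The plan expects such weeks: section 5.2.1 accepts that not everyone can always attend, and the attendance target (70% completing 6 of 10 classes) leaves room for 30% to attend five or fewer.

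If staff follow Table 3 and 6.2.6, a person who misses a class fills in no form for that week. The benchmark counts practice over 10 weeks, and an analyst cannot recover weeks for which nobody was asked. Home practice would then partly re-measure attendance, which has its own row in the same table. Participants who practise in their cells but miss classes would look like non-practisers, and the team could draw the wrong lesson about the home-practice component for the larger trial.

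**Working it through.** The plan gives no calculation for this benchmark, so there is no stated figure to reproduce.

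**Inputs from the documents.** 40 participants randomised 1:1 (DSMP 7.2) gives 20 in the yoga arm, and 70% of 20 is 14. The criterion is 6 of 10 weeks (9.5.1), with one class a week for 10 weeks.

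**Assumptions.** Each form covers one week, forms are completed only after attended classes, and a week without a form counts as no practice.

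**Step 1: ceiling, with no model of behaviour.** A participant attending k classes has at most k recorded practice weeks.

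- k of 5 or fewer: 6 weeks cannot be reached.
- k = 6: all six forms must show enough practice.
- If exactly 14 of 20 attend six or more, so that attendance just meets its own target, recorded success is at most 14/20 = 70%. All 14 must succeed for the home-practice target to be met.

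**Step 2: how far recorded success falls below true success.** This is illustrative; the documents fix none of these inputs. Let a be the chance of attending in a given week, 0.8 the chance of enough practice in an attended week, and r the chance of enough practice in a missed week, with weeks independent.

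- True success = P(Bin(10, 0.8a + r(1−a)) ≥ 6)
- Recorded success = P(Bin(10, 0.8a) ≥ 6)

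The value a = 0.627 is the one at which P(Bin(10, a) ≥ 6) = 0.70.

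| a | Recorded | True, r = 0 | True, r = 0.3 | True, r = 0.8 |
|---|---|---|---|---|
| 0.627 | 38.2% | 38.2% | 66.7% | 96.7% |
| 0.8 | 72.9% | 72.9% | 85.0% | 96.7% |
| 0.9 | 88.2% | 88.2% | 92.2% | 96.7% |

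For example, at a = 0.627 and r = 0.3 the weekly chance is 0.627×0.8 + 0.373×0.3 = 0.614, and P(Bin(10, 0.614) ≥ 6) = 0.667.

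The chance that 14 or more of 20 are recorded as successes is 0.4%, 72% and 99.4% down the three rows. At a = 0.627 the chance based on true practice is 0.4% for r = 0, 48% for r = 0.3 and almost 100% for r = 0.8.

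**Step 3: clustered attendance.** Suppose 70% of participants attend 9 classes and practise in 80% of all weeks, while 30% attend 2 classes and practise in a share q of all weeks.

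- Recorded success = 0.7 × P(Bin(9, 0.8) ≥ 6) = 0.7 × 0.914 = 64%, whatever q is.
- True success = 0.7 × 0.967 + 0.3 × P(Bin(10, q) ≥ 6).

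| q | True | Gap |
|---|---|---|
| 0 | 68% | 4 points |
| 0.3 | 69% | 5 points |
| 0.5 | 79% | 15 points |
| 0.8 | 97% | 33 points |

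**The case against.** **The conflict is narrow.** Section 6.2.6 does not name the homework form, and 7.4 and Table 4 concern injuries only. For homework, the tension is Table 3 with the general sentence in 6.2.6 against the explicit weekly statement in 9.1.2. Sections 8 and 9.5.1 keep assessments going after discontinuation, which leans towards weekly collection. This stands as a matter of intent, but neither section names a contact at which a class-triggered form would be completed once someone stops attending.

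**The deciding fact is not visible.** The recall window would be on the form or in the manual of procedures, and neither is among the documents. A form asking about practice since the last class could recover gaps between attended classes, though not the weeks after the last one. This stands, and it limits the point to a conditional one.

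**Practice is probably linked to attendance.** Section 5.2.1 gives out practice assignments in class. If absent participants do not practise, counting their missed weeks as no practice is simply correct. This stands.

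**Other checks exist.** Attendance has its own target and is reviewed at least monthly (DSMP 7.1.2), and the adapted IPAQ asks about yoga practice. These would help explain a miss, but they do not supply the weekly counts. A missed target leads first to investigation and discussion, so the consequences are soft.

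**A stronger reading that the documents do not support.** A reader might infer that the plan leaves the scoring rule wide open, so that the same behaviour could fail outright or pass almost surely depending on whether success is judged on all 10 weeks or only on answered weeks. But the criterion is a count out of 10 weeks, and the analysis is intent to treat, which points to a fixed denominator. A proportion-of-answered-weeks rule appears nowhere in the documents. The real gap is in collection.

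**Conclusion.** The point holds in conditional form. The documents describe two collection schedules that differ in missed-class weeks. If the class-triggered one is followed with one-week forms, practice in those weeks is unrecorded, nobody attending five or fewer classes can meet the criterion, and recorded success is capped at 70% when exactly 14 of 20 attend six or more.

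The ceiling rests only on the one-week recall window, the literal 10-week count and all 20 yoga participants as denominator. The size of any understatement rests on assumed behaviour. In the illustrations it runs from zero to a few points when absent participants do not practise, up to about 59 points (96.7% against 38.2%) when attendance is only just at its target and practice while absent is as frequent as at other times. Neither extreme can be called likely from the documents.

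A reader might also infer a safety failure from the injury item. The documents do not support that: SAFTEE is used to "inquire about the occurrence of AE/SAEs during the previous 8-10 weeks", and the next attended class and spontaneous reports also capture injuries. That gap is minor.

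Overall this is an improvement worth considering. It is more than a wording matter because data not collected cannot be restored at analysis.

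**What to change.** Reconcile Table 3, 6.2.6, 7.4, 9.1.2 and Table 4 so that the homework and yoga-injury items cover each of the 10 weeks regardless of attendance. Have the research assistant complete a missed week at the next existing contact (the next class, or the week 5 or week 10 assessment) and flag it as recalled.

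For scoring, state that the denominator is all randomised yoga participants and 10 weeks, and that weeks still unanswered count as no practice. Report the number of weeks answered and the number recalled. A sensitivity result on answered weeks is optional; if used, its threshold should be fixed in advance.

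The cost is a few added questions at contacts that already take place, plus a wording amendment. The downside is recall error: about five weeks for someone who stops attending, and longer if a visit is late, since 6.2.6 still accepts data collected after the assessment window. Weeks will also stay missing for anyone who misses the week 10 assessment, where the retention target is 80%; non-attenders may be over-represented among them. Flagging recalled weeks and reporting the counts makes both limits visible.
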